**Evaluation of the Effect of Black Tea Extract on the
Primary Bleeding Cessation after Molar Extraction:
A Randomized Controlled Trial**

NCT number: NCT06687824

Date: 1/5/2025

1. Study Objectives

1.1 General Objectives:

To evaluate the effect of black tea extract on bleeding cessation after molar extraction

1.2 Specific Objectives:

- a) To determine the bleeding cessation time with used of normal sterile gauze with 0.5% povidone iodine (PVI)after molar extraction.
- b) To determine the bleeding cessation time with used of black tea extract-impregnated (BTEI) sterile gauze after molar extraction.
- c) To identify adverse effect of BTEI sterile gauze and PVI sterile gauze on post-extraction sites.
- d) To compare the bleeding cessation with used of the BTEI sterile gauze and PVI sterile gauze on post-extraction area.

2. Research Hypotheses

There is no difference of bleeding cessation time between BTEI gauze and 0.5% PVI sterile gauze.

3. Methodology

3.1 Preparation of Black Tea-Extract Impregnated Sterile Gauze

For the preparation of black tea-extract impregnated (BTEI) gauze, 5 gauzes were prepared for each time. High-performance liquid chromatography (HPLC) was used to determine the tannin concentration in the black tea extract, which was 4.67 % w/w. 10 grams of black tea-extract powder was mixed with 24ml of saline using magnetic stirrer with 200 rpm for 10 minutes to achieve 18.67 mg/mL of tannin concentration in the solution. 5ml of solution was measured and inserted into sterilized ice cube tray. Sterile gauzes were soaked into each cube. It was covered with sterile lid and stored in 4 °C refrigerator for 24 hours for uniform absorption for each gauze. Then, the gauzes were sent for ultraviolet germicidal irradiation. 10 minutes for 1 side and flipped the gauzes for another 10 minutes. After that, the gauzes were folded and packed into sterile sealed plastic bag until usage.

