3.2 Preparation of 0.5% Povidone Iodine Impregnated Sterile Gauze

5 gauzed were prepared at the same time together with BTEI gauzes. 5ml of 0.5% povidone iodine solution was inserted into each cube followed by soaking a gauze into each cube. The gauzes were stored in refrigerator and sent for ultraviolet germicidal irradiation together with BTEI gauzes.

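### Does the stated tannin strength of 18.67 mg/mL contradict the recipe of 10 g of extract in 24 mL of saline?

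*Combined protocol and SAP*

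**What the plan says.** Section 3.1 describes the test gauze. HPLC was used to "determine the tannin concentration in the black tea extract, which was 4.67 % w/w". For the solution, 10 g of the powder was "mixed with 24ml of saline using magnetic stirrer with 200 rpm for 10 minutes to achieve 18.67 mg/mL of tannin concentration", and the strength is stated for the finished solution ("to achieve 18.67 mg/mL of tannin concentration in the solution"). Batches were small ("5 gauzes were prepared for each time"), and "5ml of solution was measured and inserted into sterilized ice cube tray", with a gauze soaked in each cube. Section 3.1 does not say in so many words that the 5 mL is per cube. Section 3.2 does say so for the control gauze made alongside: "5ml of 0.5% povidone iodine solution was inserted into each cube".

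Neither section gives the final volume of the tea solution or mentions making it up to a set volume. Section 3.1 reports an assay of the extract but describes none of the prepared solution.

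**The concern.** The only liquid volume in the tea recipe is 24 mL. Dividing the tannin by that volume does not give 18.67 mg/mL, and 24 mL of liquid is 1 mL short of five 5 mL portions. On that reading the powder mass, the volume, the batch size and the strength cannot all be right.

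The figure is the only stated strength of the test solution. Readers will attach the trial's result to it, and anyone repeating the work may aim for it. If it were wrong, the product would be misdescribed. Someone following the recipe also cannot tell whether to add 24 mL of saline or to make the mixture up to 25 mL.

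**Working it through.** **Inputs (section 3.1, with the per-cube volume made explicit in section 3.2).** Powder 10 g; tannin 4.67% w/w (unrounded value between 4.665% and 4.675%); saline added 24 mL; 5 gauzes per batch; 5 mL of solution per cube; stated strength 18.67 mg/mL.

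**Formula.** Concentration = powder mass × tannin fraction ÷ volume of solution.

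**Tannin in a batch.** 10,000 mg × 0.0467 = 467 mg.

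**Reproducing the stated figure.** Volume dispensed = 5 × 5 mL = 25 mL. 467 ÷ 25 = 18.68 mg/mL. Rounding of the tannin content gives 466.5 ÷ 25 = 18.66 to 467.5 ÷ 25 = 18.70, which contains 18.67. In reverse, 467 ÷ 18.67 = 25.01 mL. The batch size and the stated strength therefore point to the same volume.

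**Using the saline volume instead.** 467 ÷ 24 = 19.46 mg/mL (rounding range 19.44 to 19.48), and 19.46 ÷ 18.67 = 1.042, or 4.2% higher. Rounding cannot close that gap. This divisor is correct only if 10 g of powder adds no volume at all.

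**How the answer depends on the powder.** The documents give no figure for the volume that the powder adds, so the first column below is an assumption, shown as a range. Final volume = 24 + 10 × (mL added per g).

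| Added volume (mL/g) | Final volume (mL) | Concentration (mg/mL) | Against 18.67 | Tannin in 5 mL (mg) |
|---|---|---|---|---|
| 0 | 24 | 19.46 | +4.2% | 97.3 |
| 0.1 | 25 | 18.68 | +0.1% | 93.4 |
| 0.3 | 27 | 17.30 | −7.4% | 86.5 |
| 0.5 | 29 | 16.10 | −13.7% | 80.5 |
| 0.7 | 31 | 15.06 | −19.3% | 75.3 |
| 0.8 | 32 | 14.59 | −21.8% | 73.0 |

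The stated strength corresponds to the second row, where the powder adds about 1 mL in all.

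**The five wells.** The cubes receive solution, not saline. Every row of the table from 0.1 mL/g upward gives at least 25 mL, so the 24 mL of saline does not by itself show a shortfall. Even with no added volume, sharing the batch equally gives 24 ÷ 5 = 4.8 mL per gauze and 4.8 × 19.46 = 93.4 mg of tannin. That is the same amount as 5 mL at the stated strength (5 × 18.67 = 93.4 mg).

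**Where the figure is used.** The hypothesis (section 2) compares bleeding cessation time between the two gauzes. The primary outcome (section 4.1.1) is the effect of the tea gauze on bleeding cessation. The analysis (section 4.3) compares proportions with haemostasis at 2, 5 and 7 minutes by a chi-square test. None of these takes the concentration as an input. There is one tea arm, and no dose-response question is asked.

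**The case for a change.** The strongest case for acting is that 25 mL is inferred and never stated as the volume of the solution. Starting from 24 mL of saline, it is reached only if 10 g of powder adds about 1 mL (0.1 mL per g), and nothing in the documents supports that value. With no assay of the prepared solution described, 18.67 mg/mL has no independent support. The point applies to every batch of tea gauze, and checking it would take one line.

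These facts stand: the final volume is unstated, and the step from 24 mL to 25 mL is undocumented. They do not show a wrong strength. A figure of 19.46 mg/mL rests on zero added volume, which is equally undocumented, and the larger departures in the table rest wholly on assumed values. Depending on the assumption, the true strength could lie above, at or below the stated one, so no error in a known direction has been shown. The strength is also not all that a reader has to go on: section 3.1 gives the powder mass, its tannin content, the saline volume and the volume dispensed.

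**Conclusion.** The concern does not call for a change to the plan. The stated 18.67 mg/mL reproduces within rounding on a 25 mL solution, the volume implied by five gauzes at 5 mL each. The only departure that can be computed from the documents' own figures is 4.2%, and it needs the powder to add no volume. This conclusion assumes that the 5 mL is per cube for the tea gauze, as section 3.2 says for the control, and that all tea gauzes were made by the one recipe described.

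What remains is a gap in the description of the product. The 24 mL of saline, the five 5 mL portions and the 18.67 mg/mL must be reconciled against the batch records, and the final volume given, when the product is described in the report. The documents do not establish which strength was actually used, and no view is taken on it here. Whichever figure the records support, the allocation, the outcome, the test and the comparison between the arms stay the same.

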3.2 Preparation of 0.5% Povidone Iodine Impregnated Sterile Gauze

5 gauzed were prepared at the same time together with BTEI gauzes. 5ml of 0.5% povidone iodine solution was inserted into each cube followed by soaking a gauze into each cube. The gauzes were stored in refrigerator and sent for ultraviolet germicidal irradiation together with BTEI gauzes.

3.3 Study Design and Intervention

This is a randomized controlled trial performed in Manipal University College Malaysia's (MUCM) Oral and Maxillofacial department (OMFS), from April to December 2024. The study protocol was approved Research Ethics Committee of MUCM (MUCM/ Research Ethics Committee- 042/2023). The trial is registered with National Clinical Trial Network with registration number NCT06687824. Informed consent from all participants was collected prior commencement of study. After selection of patient according to inclusion criteria and exclusion criteria, the demographic details (age, gender) of participants were recorded. Participants that are sensitive to black tea, use of complementary medical methods within the past month, having history of exposure of surgery site to radiation and use of antibiotic, corticosteroid, anticoagulant and contraceptive drug over the past month were excluded from the study. After exclusion of participants, we included participants that were age ≥ 18 years old and included in American Society of Anaesthesiologist (ASA) I and II. Those who met the inclusion and exclusion criteria were randomly selected and allocated into Group A and Group B using block randomization with block size 4.

After patient selection and allocation, the extraction site was anaesthetized with mepivacaine hydrochloride 2% / adrenaline 1:100,000 and molar was extracted with simple

extraction without odontotomy, flap incision, flap elevation and bone removal. Time of extraction was within 20 minutes. After irrigating the socket with 0.5% povidone iodine solution, BTEI gauze was applied for intervention group and PVI gauze for control group. The primary bleeding cessation state was evaluated at 2, 5 and 7 minutes. The result was investigated and recorded as <2, 2-5, 6-7 and > 7 minutes. When the bleeding stopped, the participant was discharged and a new gauze was given and participant was instructed to bite the gauze for 1 hour. 3 days later, all participants were contacted for follow-up assessment via phone to evaluate the presence of adverse effect in all participants.

4. Statistical Analysis Plan (SAP)

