4.2 Analysis Population

After randomization, there was no dropouts, Intent-to-Treat (ITT) and Per Protocol (PP) population were identical which was 44 participants, 22 participants for each group.

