4.3 Statistical Methods

The demographic details of the participants were analysed using IBM SPSS Statistics version 26. The primary bleeding cessation time at post-extraction site after using BTEI gauze and PVI gauze was assessed at 2,5 and 7minutes post-extraction and recorded using categorical method. The proportion of participants in each group achieving haemostasis at each time point will be compared using Chi-square test. A two-tailed p-value of less than 0.05 will be considered statistically significant. The assumption for the Chi-square test will be assessed prior to analysis.

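### Does allocating before the extraction, with no concealment or masking described, require a change to the analysis of bleeding at 2, 5 and 7 minutes?

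*Combined protocol and SAP*

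**What the plan says.** Section 3.3 gives the order of events. Participants are "allocated into Group A and Group B using block randomization with block size 4". Then: "After patient selection and allocation, the extraction site was anaesthetized with mepivacaine hydrochloride 2% / adrenaline 1:100,000 and molar was extracted". The assigned gauze comes later: "After irrigating the socket with 0.5% povidone iodine solution, BTEI gauze was applied for intervention group and PVI gauze for control group". The outcome follows: "The primary bleeding cessation state was evaluated at 2, 5 and 7 minutes". The section also reports simple extractions and adds: "Time of extraction was within 20 minutes".

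Section 4.2 reports: "After randomization, there was no dropouts, Intent-to-Treat (ITT) and Per Protocol (PP) population were identical which was 44 participants", 22 in each group.

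Section 4.3 sets the analysis: "The proportion of participants in each group achieving haemostasis at each time point will be compared using Chi-square test". The decision rule is: "A two-tailed p-value of less than 0.05 will be considered statistically significant". The only further check named there concerns the assumptions of the chi-square test.

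No section says how the sequence was concealed, whether operator, participant or assessor was masked, who judged that bleeding had stopped, or by what criterion. The sealed bag in section 3.1 is sterile packaging for the gauze. Section 3.2 has the two kinds of gauze stored and irradiated together, but does not present this as masking.

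**The concern.** Whether a socket has stopped bleeding is a judgement. If the operator knew the arm, the extraction could have been done differently by arm. If the assessor knew it, a borderline socket could have been called differently by arm. The arm was fixed before either event, and fixed blocks of 4 are partly predictable to anyone who knows the earlier assignments.

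At 22 per arm the chi-square verdict can turn on one or two participants, and section 4.3 contains nothing that looks at arm-dependent judging. A reader who sees p < 0.05 at one of the three time points could not tell how far it depends on a few unprotected calls.

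A smaller point goes with this: section 4.2 takes the ITT and PP populations as identical because nobody dropped out, although absence of dropouts does not by itself show absence of protocol deviations.

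**Working it through.** **Inputs.** From the documents: 44 participants, 22 per arm (4.2); blocks of 4 (3.3); chi-square test at each time point, two-tailed 0.05 (4.3). Assumed, because the documents give no rates: true haemostasis of 30%, 50% or 70% in both arms, and misjudging rates of 10% or 20%.

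**1. The plan's own split.** 44/4 = 11 complete blocks, and 11 × 2 = 22 per arm. It reproduces.

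**2. Predictability of the blocks.** The six 1:1 sequences of length 4 leave 2, 2, 1, 1, 1 and 1 assignments certain in advance: 8/6 = 1.33 of 4 (33%), or about 14.7 of 44. The best guess is right with probability 1/2, 2/3, 2/3 and 1 at the four positions, which averages 70.8%. This applies only to someone who knows the earlier assignments.

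**3. Effect of leaning judgements.** With a and b stopped in the two arms, the uncorrected statistic is X² = 44(a − b)² / [(a + b)(44 − a − b)]. The rejection rate is the sum of binomial probabilities over all 23 × 23 outcomes with p < 0.05. For misjudging at rate e in both arms toward the tea gauze, the observed rates are p + e(1 − p) and p(1 − e). For misjudging in the tea arm only, they are p + e(1 − p) and p. There is no true difference.

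| Misjudging | p = 30% | 50% | 70% |
|---|---|---|---|
| none | 4.8% | 4.9% | 4.8% |
| both arms, 10% | 10.4% | 10.0% | 10.4% |
| both arms, 20% | 27.8% | 26.2% | 27.8% |
| tea arm only, 10% | 7.3% | 6.1% | 5.4% |
| tea arm only, 20% | 15.2% | 9.9% | 7.2% |

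**4. Tipping counts.**
- 17 v 10: X² = 44 × 49/(27 × 17) = 4.70, p = 0.030. One change gives 17 v 11: 44 × 36/(28 × 16) = 3.54, p = 0.060.
- 18 v 10: X² = 44 × 64/(28 × 16) = 6.29, p = 0.012. Two changes are needed; 18 v 12 gives 44 × 36/(30 × 14) = 3.77, p = 0.052.
- 20 v 10: X² = 44 × 100/(30 × 14) = 10.48, p = 0.001. Four changes are needed.

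Starting from equal counts, more is needed: from 11 v 11, seven changes in one arm (18 v 11, p = 0.026).

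**5. What a guard on the tipping count would do.** Suppose a difference were not called established when two or fewer changed judgements undo it. Over all outcomes at 22 v 22:
- The largest p that survives is 0.0066, for example 16 v 7: X² = 44 × 81/(23 × 21) = 7.38.
- Some smaller p-values still fail: 7 v 0 has X² = 44 × 49/(7 × 37) = 8.32, p = 0.0039, yet 7 v 2 gives 44 × 25/(9 × 35) = 3.49, p above 0.05.
- With no bias, the false-positive rate falls from 4.8-4.9% to 0.6-1.0%.
- With no bias, power falls from 78% to 55% for 70% v 30%, and from 67% to 30% for 90% v 60%.

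**The case for a change.** The best case for acting is that the omissions are certain and the response is cheap. Concealment, masking and assessor are nowhere described, the primary outcome is a judgement, and one or two calls can decide the verdict. A tipping count needs no assumed misjudging rate and no new data, and section 4.3 still speaks of the comparison as something to come. With no true difference and no misjudging, 80-89% of results below 0.05 would be undone by two or fewer changes, so a guard there falls where most chance findings lie.

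The omissions stand, and so does the arithmetic. The step to a changed plan does not.
- At fixed sample size the count largely restates the p-value. It cannot show whether anyone was masked, whether any judgement leaned, or whether extractions were done differently by arm.
- The guard works only by replacing the stated two-tailed 0.05 with a threshold near 0.005, after conduct ended in December 2024. Catching most chance findings is what any stricter threshold does.
- A cut-off of two rests on one assumed model: 10% misjudging, in both arms, always toward the tea gauze, which gives 22 × 0.10 = 2.2 expected misjudged participants. With the same 10% in the tea arm only, the false-positive rate is 5.4-7.3% and does not double.

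**Conclusion.** No change to the plan. Allocation before a procedure is ordinary and does no harm when concealed. The documents neither say the trial was open nor show that the operator or assessor knew the arm, and the labels Group A and Group B could have been coded. What is missing is a description: how the sequence was concealed, who was masked, when the operator learned the arm, who judged the bleeding and by what criterion. Authors supply this when they report, and if operator or assessor was unmasked they name it as a limitation of the primary result. Supplying it alters no analysed number.

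The possible size is real but conditional: about 10% false positives instead of 4.8-4.9% if 10% of judgements leaned in both arms, and 26-28% if 20% did. These rates, and the haemostasis rates of 30-70%, are assumptions; none is shown to have occurred. A tipping count may be given as a descriptive extra, but it changes no result. Using it to withhold a conclusion would cost 23 percentage points of power (78 − 55) for 70% v 30% and 37 (67 − 30) for 90% v 60%, and would leave any difference in the extraction itself untouched.

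Revealing a concealed allocation just before the gauze is placed could help only a repeat trial. The ITT and PP remark also changes nothing: sections 3.3 and 4.2, read together, indicate that all 44 were kept and met the stated extraction limits.

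### Do mismatched time bins and an unstated time zero leave the haemostasis proportions at 2, 5 and 7 minutes undetermined?

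*Combined protocol and SAP*

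**What the plan says.** Section 3.3 gives the order of events. The socket is irrigated and the gauze placed: "After irrigating the socket with 0.5% povidone iodine solution, BTEI gauze was applied for intervention group and PVI gauze for control group". The checks come next: "The primary bleeding cessation state was evaluated at 2, 5 and 7 minutes". The result goes into one of four bins: "The result was investigated and recorded as <2, 2-5, 6-7 and > 7 minutes". The participant is discharged once bleeding has stopped. No sentence links a check to a bin, and section 3.3 names no time zero.

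Section 4.3 describes the outcome as "assessed at 2,5 and 7minutes post-extraction and recorded using categorical method". The same sentence begins by placing the assessment after use of the gauzes. The analysis is then stated: "The proportion of participants in each group achieving haemostasis at each time point will be compared using Chi-square test". The significance rule is "A two-tailed p-value of less than 0.05 will be considered statistically significant". Section 4.2 gives the analysis set, "which was 44 participants, 22 participants for each group", with no dropouts.

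**The concern.** Section 4.1.1 names the primary outcome without a metric, so sections 3.3 and 4.3 carry its whole operational definition. Three things in them look wrong.

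- **Bins against checks.** A socket first seen dry at the 2-minute check is a success at 2 minutes for the analysis, yet the bin containing the value 2 is 2-5. Times between 5 and 6 minutes have no bin. With 22 per arm, one participant is 1/22 = 4.5 percentage points, so one boundary case could matter.
- **Interval or cumulative.** The bins are intervals. Comparing one interval between arms penalises the faster gauze, whose participants have already gone into an earlier bin.
- **Clock.** If minutes run from extraction, irrigation and placement time counts as treatment time, and the 2-minute check contains less than 2 minutes of gauze exposure.

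If these defects were real, the primary comparison could turn on an unwritten coding choice.

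**Working it through.** The documents give no sample-size or power figure to reproduce. Inputs taken from them are the check times and bins (section 3.3), 22 per arm (section 4.2), and the chi-square test at two-sided 0.05 (section 4.3). All outcome counts below are assumed, because the documents report none.

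**1. What the schedule can observe.** A stop is seen only at a check.

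| First check at which the socket is dry | True stopping time | Bin |
|---|---|---|
| 2 min | up to 2 | <2 |
| 5 min | after 2, up to 5 | 2-5 |
| 7 min | after 5, up to 7 | 6-7 |
| none | after 7 | >7 |

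No check comes before 2 minutes, so the <2 bin can be filled only from the 2-minute check. On the literal reading it would be empty in both arms, and a results table would show that at once. A stop at 5.5 minutes is first seen at 7 and goes to 6-7, so the apparent gap loses nobody.

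**2. Are the three proportions recoverable?** Let the bin counts in an arm be a, b, c, d with a + b + c + d = 22. The cumulative counts are a at 2 minutes, a + b at 5 and a + b + c at 7. The number of possible splits is C(25,3) = 25 × 24 × 23 / 6 = 2300. Enumeration gives 2300 distinct cumulative triples, so the mapping is one-to-one.

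**3. Interval against cumulative.** Assume tea 15/5/1/1 and povidone iodine 5/12/4/1. Uncorrected chi-square = N(ad − bc)² / (product of the four margins), where a to d are now the 2×2 cells.

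- The 2-5 bin alone, 5/22 v 12/22: 44 × 154² / (22 × 22 × 17 × 27) = 4.70, p = 0.030, against tea.
- Cumulative by 5 minutes, 20/22 v 17/22: 44 × 66² / (22 × 22 × 37 × 7) = 1.53, p = 0.216, in favour of tea.

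The reversal is genuine arithmetic, but the first line is not the stated analysis. Section 4.3 compares participants achieving haemostasis at each time point. Discharge at haemostasis and the 22 per group in section 4.2 both fit carrying early successes forward over all randomised participants.

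**4. One boundary participant.** Move one participant in the first arm from dry at 2 minutes to the 2-5 bin (uncorrected chi-square):

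| Dry at 2 min | p before | p after |
|---|---|---|
| 14/22 v 7/22 | 0.035 | 0.069 |
| 12/22 v 5/22 | 0.030 | 0.060 |
| 15/22 v 7/22 | 0.016 | 0.035 |
| 10/22 v 4/22 | 0.052 | 0.099 |

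The result crosses 0.05 in two of the four cases. This requires one participant to be coded differently from others with the same finding.

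**5. Clock.** Assume exponential stopping with a median of 3 minutes from gauze placement, and a lag L between extraction and placement. The proportion dry at t is 1 − 2^(−(t − L)/3).

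| L (min) | t = 2 | t = 5 | t = 7 |
|---|---|---|---|
| 0 | 37% | 69% | 80% |
| 0.5 | 29% | 65% | 78% |
| 1 | 21% | 60% | 75% |

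The levels move, but irrigation precedes gauze in both arms. If the gauzes work equally and the lag has the same distribution in each arm, the proportions are equal at every check on either clock. The test of no difference therefore keeps its meaning.

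**The case for a change.** The best argument for a change is that a primary outcome should not need a reader to infer its coding rule. The <2 label is strict although the finding is made at 2 minutes. The word cumulative does not appear. With the counts assumed above, a third reading (only those still bleeding) would give 5/7 v 12/17, p = 0.97 at 5 minutes, so three readings give three answers. The documents do not describe whether the assessor was blinded, and a loose boundary leaves room for discretion. Repair needs only a few words.

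Part of this stands. The labels are imprecise, the rule is unwritten and time zero is never explicitly defined. But the alternative readings are not equally open. The literal one leaves a listed bin permanently empty, and the interval and still-bleeding comparisons do not match the quantity named in section 4.3. The clock conflict is weaker than it looks: section 3.3 implies an origin by sentence order without stating one, and section 4.3 uses its extraction wording in a sentence that also places assessment after gauze use. Assessor blinding is a separate question that bin labels do not settle.

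**Conclusion.** No change to the plan follows. This is a clerical mismatch of labels and a gap that an analyst fills in the obvious way: the bin records the first check at which the socket is dry, and each time-point proportion is cumulative over 22 per arm. On that reading all three proportions are exactly determined, and rewording alters no count, test or conclusion. Section 3.3 gives April to December 2024 as the trial period and section 4.2 already reports the final numbers. A new data field or a newly chosen time zero therefore cannot reach participants already assessed; the authors could only describe the clock and coding they used.

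This rests on two assumptions: that staff coded consistently by first dry check, and that the interval from extraction to gauze was similar in the two arms. The documents contradict neither. If check-level records showed inconsistent coding at 2 minutes, the sensitivity in step 4 would become relevant. The clock effect, up to 16 percentage points at 2 minutes for a 1-minute lag (37% to 21%), depends on an assumed median, distribution and lag. It concerns how 2 minutes is interpreted, with no bias between arms shown.
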